#### **11.6 UNSCHEDULED VISIT(S) FOR ADVERSE EVENT OR SPONTANEOUS REPORT OF VISUAL DISTORTION(S)**

A visit is considered an unscheduled study visit when it occurs other than at the specified 1- or 6-month study visits AND at which an ocular adverse event is reported OR if the subject has a spontaneous report of any of the 5 defined visual distortion items of interest (lines that slant, tilt or separate, flat surfaces appearing curved, objects appearing further away or closer than they actually are, objects appearing to have a different size or shape or physical discomfort related to vision as defined in Section 6.0) or of blurred or hazy vision at 1 month postoperatively or later. For example, if the subject is seen for a routine (non-study) 3-month follow-up visit and there are no ocular adverse events or any spontaneous reports of visual distortion(s) of interest or of blurred or hazy vision at 1 month postoperatively or later, this would NOT be captured on an unscheduled visit form. If however, the subject commented on a visual distortion as listed above or an ocular adverse event was noted at this visit, this visit would be captured on an unscheduled visit form.

During the study period, if a serious or device-related adverse event occurs, per Section 12.0, details of the event are to be captured on an adverse event CRF and the exam details are to be captured on the appropriate visit CRF (i.e., 1-month, 6-month, 1-year or unscheduled). The event will be followed up as necessary and details captured on adverse event follow-up CRFs until resolution.

If the event results in an IOL repositioning procedure (secondary surgical procedure), the PRVDQ questionnaire is to be administered and, for subjects with toric IOLs, keratometry and toric IOL axis measurements are to be performed PRIOR to the IOL repositioning procedure for evaluation of visual distortions arising from IOL misalignment.

If a subject reports a visual distortion at an unscheduled visit, the PRVDQ questionnaire is to be administered, and, for subjects with toric IOLs, keratometry and toric IOL axis measurements are to be performed.

Data to be collected on adverse event and/or unscheduled visit forms (due to ocular adverse event or spontaneous report of visual distortion) include, as applicable:

- ❖ Adverse event, date of onset and classification
- ❖ Prognosis and treatment
- ❖ Questionnaire - in the event of a spontaneous report of visual distortion or prior to an IOL repositioning procedure
- ❖ Manifest refraction (Snellen), if performed
- ❖ Uncorrected and best-corrected distance visual acuity (Snellen), if performed
- ❖ Keratometry, for toric IOLs only- in the event of a spontaneous report of visual distortion or prior to an IOL repositioning procedure
- ❖ Intraocular pressure, if performed
- ❖ Toric IOL axis measurement by dilated slit-lamp examination, for toric IOLs only (Refer to Appendix C for measurement instructions) - in the event of a spontaneous report of visual distortion or prior to an IOL repositioning procedure
- ❖ Slit-lamp examination for medical and/or lens findings (e.g., IOL rotation), if performed
- ❖ Dilated fundus exam, if performed
- ❖ Ocular medications

## 11.7 SUBJECT FOLLOW-UP AND DISCONTINUATION

Every attempt will be made to gather complete follow-up data for all treated subjects. If a subject has a confirmed report of severe visual distortion(s) per the questionnaire, prior to the 6-month exam, every effort is to be made to ensure that subject returns for the 6-month exam. The investigative site shall make a minimum of at least three attempts

(phone calls/emails and/or letters) to locate missing subjects. It is the responsibility of the investigator to provide complete follow-up data to AMO for each subject.

#### SUBJECT FOLLOW-UP

To minimize subjects lost to follow-up, subjects will be provided compensation for their time and participation in the study at the 1- and 6-month postoperative exams. Additionally, sites will be compensated for completion of the 1- and 6-month exams and will be provided frequent listings of upcoming 1- and 6-month subject examinations as well as follow-up reminder cards to send to the subjects. It is anticipated that at least 90% of subjects will be available for the 6-month study visit (i.e., no more than a 10% lost-to-follow-up rate at 6 months postoperatively).

#### SUBJECT DISCONTINUATION

The investigator should notify AMO prior to discontinuing a subject from the study. If a subject is discontinued from the study, the investigator will, if at all possible, have the subject return for a final study visit. An Exit CRF is to be completed for each subject exiting the study indicating the reason for early termination.

Subjects should be discontinued from the study only if irretrievably lost to follow-up or for unavoidable reasons such as subject moved/unable to locate, subject uncooperative/refuses to return, subject died, subject ill/unable to travel, subject institutionalized. The site shall document at least three attempts (phone calls/emails and/or letters) to locate lost-to-follow-up subjects. Patients who would be traveling, relocating or otherwise unavailable for postoperative follow-up visits should not be chosen for this clinical study. In the event of unplanned subject relocation, efforts must be made by the investigator to secure follow-up information (i.e., slit-lamp examination, etc.) from the subject's new physician.

A subject may be discontinued from the study if complications occur during the first-eye surgery and the planned study lens is not implanted; however, the eye will be followed until the resolution of the complication prior to discontinuing the subject from the study. If a complication occurs during the second-eye surgery and the planned study lens is not implanted in the second eye, the subject is to be followed according to the protocol for the first eye (although data may be analyzed separately), and the second eye will be followed for safety until resolution of the complication.

In the event of a lens removal or other serious adverse event, the subject may be exited from the study; however, efforts must be made by the investigator to follow the subject until resolution of the adverse event.

## **12.0 ADVERSE EVENTS AND PRODUCT COMPLAINTS**

### **12.1 ADVERSE EVENT AND COMPLAINT DEFINITIONS**

#### ADVERSE EVENT (AE)

Any untoward medical occurrence, unintended disease or injury, or untoward clinical signs (including abnormal laboratory findings) in subjects, users or other persons, whether or not related to the IOL or the implantation procedure.

All adverse events will be recorded in the subject's case report forms. An adverse event form will be completed by the investigative site for any adverse device effect (ADE) or serious adverse event (SAE).

NOTE: Findings typical of early postoperative healing (e.g., corneal edema, cells and flare, elevated intraocular pressure, etc.) will not be considered an ocular adverse event in the first postoperative month.

#### ADVERSE DEVICE EFFECT (ADE)

An adverse event that is believed to be, probably or possibly related to the IOL or the use of the IOL.

#### PRODUCT COMPLAINT/DEVICE DEFICIENCY

Any alleged deficiency related to the identity, quality, durability, reliability, safety, effectiveness, or performance of a device after it is released for distribution. Product complaints can pertain to any marketed AMO device being used in the study as well as the study device, if marketed in another region. The investigator is to assess whether the deficiency could have led to a serious adverse event without suitable action or intervention or under less fortunate circumstances.

#### SERIOUS ADVERSE EVENT (SAE)

A serious adverse event is any (ocular or non-ocular) untoward occurrence which may or may not be related to the use of the study device that:

- ❖ results in death
- ❖ is sight- or life-threatening

- ❖ requires in-patient hospitalization or prolongation of existing hospitalization (a planned hospitalization for a pre-existing condition is not considered an SAE)
- ❖ results in permanent impairment of a body structure or body function, or
- ❖ necessitates medical or surgical intervention to prevent permanent impairment to a body structure or function
- ❖ led to fetal distress, fetal death, congenital abnormality or birth defect

#### STUDY-SPECIFIC ANTICIPATED SERIOUS ADVERSE EVENTS

The following is a list including, but not limited to, ocular adverse events that are anticipated and must be reported to AMO for this study. Any events that are unlikely but anticipated (i.e. endophthalmitis) will be reported to the FDA.

- ❖ Endophthalmitis/Intraocular infection
- ❖ Hypopyon
- ❖ Hyphema
- ❖ Lens dislocation
- ❖ Cystoid macular edema
- ❖ Pupillary block
- ❖ Retinal detachment/tear
- ❖ Persistent corneal edema
- ❖ Persistent iritis
- ❖ Persistent elevated IOP requiring treatment
- ❖ Tilt, decentration or axis misalignment resulting in secondary surgical intervention (e.g. repositioning)
- ❖ Visual symptoms requiring secondary surgical intervention
- ❖ Residual refractive error resulting in a secondary surgical intervention
- ❖ Residual lens remnants resulting in a secondary surgical intervention

**NOTE 1:** Conditions resulting in anterior chamber taps in the first postoperative week, suture removal and/or Nd:YAG capsulotomy are not considered adverse events for this study.

**NOTE 2:** For those subjects who are required to return for the 1-year study exam, conditions resulting in refractive enhancements performed after the 6-month postoperative exam are also not considered adverse events for this study and are to be reported as non-adverse event secondary surgical procedures.

**NOTE 3:** Raised IOP requiring treatment, corneal edema and iritis will only be considered serious if persistent at the final study visit (120-180 days postoperative or 330-420 days postoperative if 1-year visit is required) or sight-threatening at the time of occurrence. Treatment merely to hasten the resolution of such conditions (and not intended to prevent permanent damage to the eye) will not be reported.

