### **Serious Adverse Event (SAE)**

In the event of a sight- or life-threatening incident or serious adverse event, which may or may not be related to use of the study device, **the investigator must notify AMO immediately (no later than 48 hours after detection)** by phone and/or email and by submitting a completed Adverse Event Form as follows:

- a. Contact the following AMO personnel by phone:

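### NOTE 1 in Protocol 12.1 takes any condition behind a first-week anterior chamber tap out of adverse events with no exception for serious conditions, against the SAE definition, the anticipated-SAE list and NOTE 3, and no precedence is stated

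*Protocol*

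**What the plan says.** Four pieces of text in Protocol 12.1, and the reporting rules that depend on them, bear on an event in the first week after surgery.

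- **NOTE 1**, directly below the anticipated-SAE list: "Conditions resulting in anterior chamber taps in the first postoperative week, suture removal and/or Nd:YAG capsulotomy are not considered adverse events for this study".
- **SAE definition.** It opens with "A serious adverse event is any (ocular or non-ocular) untoward occurrence which may or may not be related to the use of the study device". Its criteria include that the event "is sight- or life-threatening" or that it "necessitates medical or surgical intervention to prevent permanent impairment to a body structure or function". It has no exception for timing or procedure.
- **Anticipated-SAE list.** It includes endophthalmitis or intraocular infection, hypopyon, hyphema and pupillary block with no time limit, and its introduction obliges sites to report listed events to the sponsor.
- **NOTE 3.** "Raised IOP requiring treatment, corneal edema and iritis will only be considered serious if persistent at the final study visit" (the visit windows follow) "or sight-threatening at the time of occurrence".

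A further note, under the definition of an adverse event, applies to the first postoperative month: "Findings typical of early postoperative healing (e.g., corneal edema, cells and flare, elevated intraocular pressure, etc.) will not be considered an ocular adverse event".

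On reporting, 12.2 requires notice of an SAE within 48 hours. Appendix E sets the same limit and begins "In the event of a sight- or life-threatening incident or serious adverse event". The medical monitor reviews serious and device-related events (16.3). SAP 4.4 tabulates adverse events at any time after surgery.

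**The concern.** Excluding a procedure from adverse events is common and usually harmless. NOTE 1 goes further, because it excludes whatever condition led to the tap. Read literally, a serious condition tapped in week 1 is not an adverse event, while other text in the same subsection calls it an SAE.

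The neighbouring notes show what NOTE 1 lacks. NOTE 3 keeps sight-threatening cases serious. NOTE 2 sends the conditions it excludes to another reporting category. Nd:YAG capsulotomy, which NOTE 1 also excludes, has its own item among the postoperative case report form contents in 11.5. A tapped condition has neither a severity exception nor a substitute route.

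Continued safety is part of the study objective (3.0), and rates of other adverse events are a listed endpoint (6.0). A classification rule that can remove serious early events bears on both, and on the information behind the suspension criteria in 19.0.

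**Working it through.** The point concerns definitions. The plan has no figure to reproduce, so the check compares texts and adds one sum on visit windows.

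**Step 1. Classify example conditions, each assumed to have led to a tap in the first week.**

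| Condition | SAE definition | Anticipated list | NOTE 3 | NOTE 1 |
|---|---|---|---|---|
| Pressure rise that meets no SAE criterion | not serious | not listed (only persistent elevation is) | not serious | not an adverse event |
| Sight-threatening pressure rise | serious | not listed unless persistent | serious | not an adverse event |
| Sight-threatening corneal edema or iritis | serious | not listed unless persistent | serious | not an adverse event |
| Intraocular infection | serious if it meets a criterion | listed | silent | not an adverse event |
| Hypopyon, hyphema, pupillary block | serious if a criterion is met | listed | silent | not an adverse event |

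The first row shows no conflict over seriousness. Every other row does, but the opposing text varies. For pressure, edema and iritis it is the SAE definition and NOTE 3. For infection and the other listed events it is the list and, where a criterion is met, the SAE definition.

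**Step 2. Look for a rule of precedence.** There is none. NOTE 1 stands directly under the list and is worded for this study, so a site can fairly take it as the specific exception. The SAE definition covers any untoward occurrence, so a site can equally take it as overriding.

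**Step 3. See whether the event would be captured another way.**

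- The first scheduled postoperative visit is 30 to 60 days after second-eye surgery (11.2). For the second eye, an event on day 7 precedes the visit by at least 30 − 7 = 23 days.
- Second-eye surgery may be up to 60 days after the first. For a first eye the visit therefore falls between 0 + 30 = 30 and 60 + 60 = 120 days after that eye's own surgery.
- Before that visit, an unscheduled visit form is opened for an ocular adverse event or for a spontaneous report of distortion or of blurred or hazy vision (11.6). The one-month qualifier applies at least to blurred or hazy vision. In either case the trigger is a symptom report; a tap alone does not open a form.
- The postoperative form contents in 11.5 include Nd:YAG capsulotomy and adverse events but have no item for taps.
- The SAP tabulates medical and lens findings at 6 months (Appendix I).

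If NOTE 1 is applied literally, a tapped week-1 condition has no other clear route into the adverse-event tables.

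**Step 4. Check the first-month note.** It covers only findings typical of healing. A sight-threatening finding need not be typical, so the note can be read together with NOTE 3 and the SAE definition. Its weakness is that it gives no criterion for what is typical. That makes it vague; it does not make it contradictory.

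**The case against.** The strongest reply is that the reporting duty does not depend on a prior classification as an adverse event. The SAE definition starts from any untoward occurrence, Appendix E requires notice of a sight-threatening incident as well as of an SAE, and the list carries its own duty to report. A site would have to pass over all of these to stay silent. NOTE 1 also groups taps with suture removal and Nd:YAG capsulotomy, which suggests it was aimed at minor postoperative procedures. The rule is the same for both lens groups, and monitors review subject files for unreported adverse events (16.2).

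Most of this stands, and it limits the finding: under-reporting is possible, not required. It does not remove the conflict. NOTE 1 is worded as a study-specific exclusion, and a monitor applying it literally would see nothing to query.

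A reader might go further and infer that the protocol exempts all raised pressure, edema and inflammation for a month. The first-month note does not support that, because it is confined to typical healing. Nor do the documents support the inference that an event outside the adverse-event definition can never reach the SAE rules: the SAE definition and Appendix E reach it directly.

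**Conclusion.** The contradiction in NOTE 1 is real and narrow. It concerns conditions tapped in the first week that threaten sight, need intervention to prevent permanent impairment, or are on the anticipated-SAE list. For these, the protocol gives opposite classifications and no precedence. What happens depends on which text a site follows.

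The size cannot be estimated. The documents do not say why taps are done, how often, or how many tapped conditions would be serious. Applying an assumed rate of early sight-threatening events to all implanted eyes would count a broader set of events than those tapped in week 1. The finding rests on one assumption: that some listed or sight-threatening conditions can lead to a first-week tap.

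The primary endpoint, taken from the 6-month questionnaire, is unaffected. The exposure is in expedited reporting, medical oversight and the adverse-event percentages.

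**What to change.** Reconcile the passages. State in NOTE 1 that its exclusion does not override the SAE definition, the anticipated-SAE list or NOTE 3. As a secondary clarification, add the same cross-reference to the first-month note. This uses only criteria already in the protocol and sets no new clinical rule. Limiting NOTE 1 to the procedure alone is not recommended, because it would turn routine tapped conditions into adverse events, which is more than reconciliation needs.

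New wording helps only events still to come. Section 20.6 says the sample size reflects subjects already enrolled at version 3.0, so many first-week windows have probably passed. Sites should therefore check, within the source review already planned under 16.2, whether any condition tapped in the first week met the existing SAE criteria or the list and was not reported. The charts should allow this, since 15.1 requires them to record postoperative medical findings and adverse events.

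The cost is two short insertions in an amendment, a communication to sites, some record checking and possibly a few more reported events.

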If a subject reported a severe visual distortion in the questionnaire or experienced an ocular adverse event at any scheduled or unscheduled study visit, uncorrected distance visual acuity, best corrected distance visual acuity, manifest refraction, slit-lamp examination and intraocular pressure measurements will also be performed.

A 1-year examination will be required only if the subject reports a severe visual distortion at the 6-month examination or experienced an IOL repositioning procedure (due to IOL misalignment during the study).

If a serious or device-related adverse event occurs at or prior to the 6-month visit, details of the event will be collected at the time of the event using an adverse event form. If the adverse event is an IOL misalignment resulting in an IOL repositioning procedure, the questionnaire is to be administered prior to the repositioning procedure to collect information regarding visual distortions, and, for subjects with toric IOLs, keratometry and toric IOL axis measurements will be performed prior to the repositioning procedure to collect data regarding the IOL misalignment.

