**DATA ANALYSIS:**

The rate of severe visual distortions as defined by the 5 items listed under primary endpoint will be compared between bilaterally-implanted toric IOL subjects and bilaterally-implanted non-toric control IOL subjects at 6 months. The frequency and proportion of toric and non-toric control subjects with severe visual distortions will be reported. Results between the toric IOL and the non-toric control IOL groups will be evaluated using a non-inferiority approach with a non-inferiority margin of 10%. Assessment of toric IOL axis misalignment will be compared to reports of visual distortions.

The frequency and proportion of secondary surgical interventions due to IOL misalignment, as well as rates for other adverse events or medical and lens findings, will be reported by treatment group. Evaluation at 6 months will include reporting by treatment groups the incidence of all adverse events, including severity for serious adverse events and adverse device effects.

Visual distortion findings, adverse events and medical/lens findings at one year will be reported for subjects who experienced a repositioning procedure during the study or for subjects who were reported with severe visual distortions at the 6-month visit.

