**11.2 VISIT SCHEDULE**

The study visit schedule for all study subjects is outlined below in **Table 4**. Additional visits may be conducted at the discretion of the investigator; however routine follow-up visits without reports of ocular adverse event(s) or spontaneous reports of visual distortion(s) are not considered study visits. Note that second-eye surgeries are intended to be performed within approximately 1 month ( $\leq 60$  days) of the first-eye surgery.

**TABLE 4  
Study Visit Schedule**

Visit	Eyes Evaluated	Exam	Visit Window
1	Both Eyes	Preoperative Exam	N/A
	First Eye Surgery		N/A
	Second Eye Surgery		Within approximately 1 month ( $\leq 60$ days) of 1 st eye surgery
2	Both Eyes	1 month	30-60 days postoperative from 2 nd implant
3	Both Eyes	6 months	120-180 days postoperative from 2 nd implant
4 a	Both Eyes	1 year a	330-420 days postoperative from 2 nd implant

a The 1-year exam is only required if a severe visual distortion was reported by the subject at the 6-month visit or if the subject underwent an IOL repositioning procedure during the study as a result of axis misalignment.

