### **20.4 OTHER ENDPOINT ANALYSES**

The frequency and proportion of medical and lens findings and adverse events will be presented for first and second eyes of toric and control subjects. The severity of all serious adverse events and adverse device effects, such as IOL repositioning procedures, through 6 months postoperatively will also be presented.

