To evaluate if IOL axis misalignment changes are associated with severe visual distortions, descriptive statistics for IOL axis misalignment will be reported for Toric subjects with and without severe visual distortions. In this study, axis misalignment is defined as the difference between the Toric IOL axis marker location from the slit lamp evaluation and the steep meridian from the postoperative keratometry measurement. This measurement is intended to evaluate toric IOL misalignment as a possible reason for severe visual distortions experienced by a subject at a specific postoperative timepoint. This axis misalignment measurement is not a measure of toric IOL rotational stability, but a measure of toric IOL alignment relative to post-surgical keratometry steep meridian [as it is known that cataract surgery can induce changes in the cornea].

4.3 Other Visual Distortion Endpoints:

The frequency and proportion with each response will also be reported for individual visual distortion items on the questionnaire and will be reported by IOL group for bilateral subjects for overall and with and without correction.

4.4 Other Safety Endpoints:

The frequency and proportion of medical and lens findings will also be reported for first and second eyes of toric (ZCT) and control (ZCB00) subjects. The frequency and proportion of adverse events at any time postoperative will also be reported.

For subjects with serious or device related adverse events or reports of severe visual distortions, additional detailed information will be provided as appropriate and may include such items as uncorrected and corrected distance visual acuity, manifest refraction, keratometry, intraocular pressure, slit-lamp and dilated fundus exam findings, ocular medications, questionnaire responses and prognosis and treatment.

5. One Month Prescription Data:

The frequency and proportion of responses to the question related to offering of spectacle or contact prescription will be reported by IOL group at the one month visit.

6. One Year Data:

Visual distortion findings, adverse events and medical/lens findings at one year will be reported for subjects who experienced a repositioning procedure during the study and for subjects who were reported with severe visual distortions at the 6-month visit.

7. Sample Size Calculations

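### NOTE 3 judges whether persistent edema, iritis or treated raised IOP is serious at a date set by study outcomes, so the 6-month serious-event counts are not defined alike for all subjects

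*Protocol*

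**What the plan says.** Protocol section 12.1, NOTE 3 (anticipated serious adverse events), states that iritis, corneal edema and raised IOP needing treatment can "only be considered serious if persistent at the final study visit (120-180 days postoperative or 330-420 days postoperative if 1-year visit is required"). The one exception is an event that is "or sight-threatening at the time of occurrence".

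The 1-year visit is conditional. The Table 4 footnote in section 11.2 says "The 1-year exam is only required if a severe visual distortion was reported by the subject at the 6-month visit", or after an "IOL repositioning procedure during the study as a result of axis misalignment". Under section 6.0 the first trigger is the primary endpoint and the second is one of the other endpoints, and all endpoints are evaluated at 6 months.

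The safety tables are tied to the same time point. The Synopsis, under Data Analysis, says "Evaluation at 6 months will include reporting by treatment groups the incidence of all adverse events", with severity for serious events. Section 20.4 says that the severity of serious events and device effects "through 6 months postoperatively will also be presented".

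SAP 4.4 uses a different window: "The frequency and proportion of adverse events at any time postoperative will also be reported". The adverse event row of SAP Appendix I does the same, although it sits in a postoperative block whose stated reporting time frame is 6 months.

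Neither document says how a condition present at month 6 is classed in the 6-month report while the subject's 1-year visit is pending.

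**The concern.** A between-group rate is interpretable only if the event is defined in the same way, over the same period, for every subject. Here the date at which persistence turns one of these conditions into a serious event depends on whether the subject reported a severe distortion or had a lens repositioned. The serious-event count at 6 months is thus partly a function of the outcomes that the study compares.

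Three consequences follow:

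- A condition present at month 6 that clears before the 1-year visit is serious in an ordinary subject and not serious in one sent on to 1 year.
- For subjects whose 1-year visit is still to come, the classification is open when the 6-month tables are produced.
- The SAP's any-time row has no cut-off, yet scheduled follow-up beyond 6 months exists only for the outcome-selected subset. That row can therefore mix 6 months of follow-up in most subjects with 12 months in a few.

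Continued safety of the lenses is part of the study objective, so the serious-event table will be read closely even though it is descriptive.

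**Working it through.** **1. The rule applied to two subjects.** Both have the same non-sight-threatening corneal edema at the 6-month visit, and in both it has cleared by day 330.

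- Subject A has no severe distortion and no repositioning. The final visit is at day 120–180, so the edema is serious.
- Subject B reported a severe distortion at 6 months. The final visit is at day 330–420, so the edema is never serious.

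A later date can also add events. A condition that arises after month 6 and is present at day 330–420 could be picked up in B, while A has no scheduled visit at which it would be seen.

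**2. Timing of the report.** The 1-year visit falls between 330 − 180 = 150 and 420 − 120 = 300 days after the 6-month visit. Section 20.7 puts the 6-month report about 3 months after the last 6-month visit. In Table 3 that report is due in January 2019, while 12-month follow-up ends in April 2019. Late-enrolled subjects sent to 1 year are therefore unclassified when the report is due.

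**3. Denominators.** The documents give no rate for these serious events. The plan's evaluable numbers (section 20.6) reproduce from 10% drop-out: 169 × 0.9 = 152.1 toric and 125 × 0.9 = 112.5 control, hence 152 and 112.

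**4. Subjects reached and largest shift.** Let d be the rate of severe distortion, r the rate of misalignment repositioning (toric only, taken as not overlapping with d), and e the share of 1-year subjects with a condition at month 6 that has cleared by 1 year.

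- Subjects sent to 1 year = n × (d + r)
- Serious events lost, in percentage points = 100 × (d + r) × e

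The 1% distortion rates come from section 20.6. The values of r (1% to 5%), e (5% to 25%) and the 5% control distortion rate are assumptions. Because every condition counted in e is taken to clear, the losses are ceilings for the chosen inputs.

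| Scenario | Toric to 1 year | Control to 1 year | Toric loss (points) | Control loss (points) | Toric minus control loss |
|---|---|---|---|---|---|
| d = 1% in both, r = 0 | 1.52 | 1.12 | 0.05–0.25 | 0.05–0.25 | 0 |
| d = 1% in both, r = 1% | 3.04 | 1.12 | 0.10–0.50 | 0.05–0.25 | 0.05–0.25 |
| d = 1% in both, r = 5% | 9.12 | 1.12 | 0.30–1.50 | 0.05–0.25 | 0.25–1.25 |
| d = 1% toric, 5% control, r = 1% | 3.04 | 5.60 | 0.10–0.50 | 0.25–1.25 | −0.15 to −0.75 |

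For example, in the third row 152 × (0.01 + 0.05) = 9.12 subjects, and the largest toric loss is 100 × 0.06 × 0.25 = 1.50 points. A positive last column means that toric events are undercounted more.

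**5. Which count moves.** Section 12.1 already lists axis misalignment leading to secondary surgery as a serious event. A repositioned subject is therefore in the any-serious-event count whatever NOTE 3 does, and only the line for the specific condition changes. In a subject sent to 1 year by distortion alone, with no other serious event, one reclassification moves the subject-level rate by 1/152 = 0.66 points (toric) or 1/112 = 0.89 points (control).

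**The case against.** The strongest reply is that NOTE 3 changes only a label. Section 12.2 has every adverse event reported, the 6-month slit-lamp exam grades edema, cells and flare in all subjects (section 11.5), and Appendix I tabulates medical findings at 6 months by group. This stands for overall adverse event incidence and for slit-lamp findings. It does not rescue the serious-event counts, which the plan presents in their own right.

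On the SAP window, section 20.1 plans cumulative complication reporting on purpose, the Appendix I block is headed 6 months, and one-year events are already reported for the 1-year subset (Synopsis; SAP section 6). Most of that stands. What is left is that the any-time row sets no cut-off of its own.

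On pending cases, section 20.7 lets the 6-month report include 1-year data to date and allows the two reports to be submitted together. That would remove the problem if it happened, but it is not assured.

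Two stronger readings are tempting, and the documents do not support them:

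- **The rule undercounts toric events.** A reader might infer this because only a toric lens has an axis to misalign. But severe distortion sends either group to 1 year, section 20.6 assumes equal rates, and section 11.5 expects control subjects to be left with refractive cylinder, which could itself cause symptoms. Only the misalignment trigger leans toric; its rate is not given, and those subjects already carry a serious event.
- **Serious safety signals are held back for months.** Sight-threatening events are serious at once, all adverse events go to the sponsor, and device-related events need an adverse event form whether serious or not. Only the remaining cases can be delayed.

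**Conclusion.** The concern holds as an inconsistency of definition. For non-sight-threatening edema, iritis and treated raised IOP, serious status in a 6-month group comparison depends on two study endpoints, and it can be unresolved when the comparison is reported. The counts may be low in whichever group has more 1-year visits. The documents fix neither which group that is nor by how much.

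At the protocol's own 1% rates, distortion affects one or two subjects per group with no expected between-group shift. Under the assumed ranges, the shift runs from 1.25 points towards undercounting toric events to 0.75 points the other way. These figures rest on assumed repositioning, persistence and control distortion rates, and apply to condition-specific serious counts. The primary non-inferiority test uses questionnaire responses and is untouched. This should be corrected because the remedy is cheap, not because the likely distortion is large.

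**What to change.** For the between-group 6-month safety tables, class persistence at the 6-month visit (day 120–180) for every subject in both groups, and report 1-year status separately for those who return. State this in NOTE 3 or in SAP 4.4. No classification would then be pending when the 6-month report is written.

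In SAP 4.4 and Appendix I, cut the between-group adverse event table at the 6-month visit and list later events separately for the 1-year subset. Keep the cumulative listing of section 20.1 as supplementary.

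The cost is a few sentences and one table cut-off. No new examination is needed: slit-lamp findings are collected in everyone at 6 months, and IOP is measured then in anyone with a severe distortion or an ocular adverse event at that visit. There are two small downsides. A few more events may be classed as serious. Subjects repositioned shortly before month 6 will also be judged sooner after their last procedure than others; a footnote giving time since last surgery deals with that. The change concerns classification and counting for tables only, and leaves patient management and event notification as they are.
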